3.10 Analyses

The results of the feasibility trial (e.g., preliminary effectiveness, feasibility and acceptability) will determine whether a full RCT (Phase II) is viable. The primary outcome, smoking abstinence for weeks 2-4 from enrolment or target quit date (for those who set a date within one week of enrolment), assessed at 1-month follow-up will be descriptively analysed in line with the one-sided confidence interval approach [47]. Consenting rate, recruitment frequency as well as attrition and adherence rate will be calculated to determine feasibility and to decide which recruitment route is most effective. Qualitative data on acceptability will be analysed using Framework analysis, guided by the Theoretical Framework of Intervention Acceptability [63], to determine themes related to barriers and facilitators to intervention acceptability, and with thematic analysis [73] to explore interview data from trial participants and research and CMHT or allied mental health professional staff. We will also conduct a simple cost effectiveness analysis to determine incremental cost-effectiveness ratios for each additional quitter in the intervention compared with control group. Secondary clinical outcome measures will be analysed using generalised linear models (with intervention allocation specified as between-group factor and time as within-group factor) to determine reductions in cigarette consumption and exhaled breath carbon-monoxide readings and changes in mental health measures from baseline to 1-month follow-up. Fidelity will be determined using an established methodology of BCT-coded audio recording of intervention sessions [66]. Finally, for all quantitative analyses (primary and secondary outcome measures), Bayes Factors will be calculated to examine for non-significant results whether the associations indicated evidence of no effect or data being insensitive to detect an effect, and for significant results, the strength of evidence [74].

3.11 Phase I Milestones

Study 1 of the project will begin on 1st November 2021, running for 12 months. The time between the award decision and month 1 will be used to begin the relevant approval processes (e.g. NHS Research Ethics Committee), to apply for adoption onto the CRN portfolio and recruit research staff. Months 1-2 will be used to complete the study set up (including intervention training, acquisition of intervention materials, and setting up of Advisory/PPI group and trial committees). Recruitment into the feasibility trial and 1-month follow-up will take place between Months 3 and 8, including qualitative interviews. Qualitative analysis will start immediately and quantitative analysis at the end of follow-up in Months 8-10. The final two months will be used to write and submit a report to YCR (months 10-12). During this time, we will also begin to recruit the additional sites across Yorkshire, to follow up on discussions that have already taken place about the willingness of sites to take part in the full RCT, if funded. We will also start the process of amending relevant approvals and seek a funding review from YCR about continuation to a full trial (see 3.14).

3.12 Intervention and procedure refinement

Based on findings from patient, research and CHMT feedback and fidelity assessment, we will review relevant aspects related to the intervention content and delivery (including staff training, conduct of research procedures and recruitment approach), and discuss potential amendments to the protocol and intervention manual to enhance acceptability with the full team, the ESCAPE PPI and the Steering group. We will use the APEASE criteria [75] and Nominal Group Technique [76] to reach consensus when reviewing intervention components for refinement and inclusion/exclusion and revise the intervention manual and materials accordingly. Due to the straightforwardness of the intervention itself, it is anticipated that changes, if any, will likely concern recruitment and delivery process and trial design, rather than intervention content.

3.13 Funding review

After Phase I, the outcome measures for the feasibility trial will be analysed and discussed with YCR regarding the feasibility of a fully powered RCT during the regular YCR KPI meetings as part of the award monitoring process. Following the feasibility trial, we request a formal "stop/go" point, and further funding for the full RCT will be determined based upon Phase I. A decision as to whether the project should progress to full trial stage will be made based on the following criteria:

a) Recruitment rate of six eligible participants per Trust with two study sites; b) Based on the confidence interval approach, an estimated effect that is larger than zero; c) Consent rate of ~15% of eligible participants, with no more than 30% attrition at follow-up; d) A clear indication of acceptability of the intervention and research process, based on qualitative and quantitative feedback measures collected from participants and research and CHMT staff (including proportion of participants from whom validated biochemical outcome measure (CO) could be successfully collected and successful training of CPN staff

to aid intervention delivery); e) Successful engagement with all co-applicant mental health Trusts for the main trial, with agreement to participate.

At this point, it may be necessary to recommend amendments to the study design/procedure to increase the chances of success of the RCT (see 3.13) and an updated sample size calculation will be conducted.

4. PHASE II - FULL RANDOMISED CONTROLLED TRIAL (MONTHS 13-48)

4.1 Aims

4.1.1 Primary research objective: To test the effectiveness of an e-cigarette starter kit as an adjunct to usual care compared with usual care alone on smoking cessation rates at 6-month follow-up among smokers with mental illness.

4.1.2 Secondary research objectives: To evaluate the impact of the intervention on smoking cessation rates at 1-month follow-up, smoking reduction at both 1-and 6-month follow-up, mental health outcomes and psychosocial measures at 6-month follow-up; to establish cost-effectiveness and assess adherence to and satisfaction with the intervention.

4.2 Design, Randomisation, Treatment groups

We intend to follow a similar approach to the feasibility trial (see Figure 1) for the design (including recruitment method), randomisation, intervention content and delivery in the full RCT, optimised based on findings from Phase I. There will be two main differences: expanded questionnaires to assess all secondary outcomes relevant for a full RCT (see 2.5), and the addition of a follow-up point at 6 months. We judged 6-months abstinence rates to be appropriate, as this is a follow-up period recommended by relevant Cochrane effectiveness reviews [37] and trial guidelines [77]. While the Phase I feasibility trial assessed abstinence at an earlier time point, relapse rates for smoking cessation treatments from one month onwards are relatively stable [78]. Therefore, it can be assumed that if the 1-month abstinence rate observed in the feasibility trial is promising (as assessed by confidence interval approach and Bayes Factor analysis), this will translate into meaningful group differences at 6-month follow-up.

4.3 Participants and procedures

Feasibility-specific data collection aside, participant selection and procedures will be the same as for Phase I, taking into account learning from the feasibility trial.

4.4 Study Sites

In addition to the Trusts involved in the feasibility trial, we will also recruit participants from at least two additional Trusts for the full RCT. Various of the 42 Trusts (including the majority of mental health Trusts in Yorkshire) involved in the SCIMITAR trial have already expressed an interest in taking part. We will also increase the number of sites per Trust from two in the feasibility trial to three (including additional sites within pilot RCT Trusts) to ensure an adequate recruitment rate to complete the full RCT within the proposed

timeframe. In line with the feasibility trial, based on a recruitment rate of six participants per Trust (with two sites), we would seek to recruit around eight participants per month per Trust (with three sites) to achieve a target sample size of 740 participants within the 22 months recruitment period (including a three-month buffer period to account for uncertainty around the exact recruitment rate).

4.5 Measures (see 3.8.1 for baseline measures)

4.5.1 Primary outcome measure

The primary outcome measure is self-reported 7-day point prevalence abstinence, assessed 6 months after study enrolment or target quit date (for those who set a target quit date within one week of enrolment) and verified by exhaled breath CO measurement. Participants will be asked whether they have smoked in the past week and only those responding that they have not had a single puff with a CO reading of less than 10 ppm will be counted as successful quitter. This is a standard outcome measure in tobacco research, recommended for research in populations where the intention to quit on a certain date is not given [79]. Smoking abstinence at 6 months is a strong predictor of long-term effects, thus enabling definitive trials to be conducted efficiently within reasonable resource [80, 81].

4.5.2 Secondary outcome measures

- 4.5.2.1 Clinical (smoking-related) outcomes: At one month, self-reported and CO-verified smoking abstinence rates, 2-4 weeks from enrolment or target quit date (whichever is later) will be recorded. Continuous abstinence at 6-month follow-up will be defined as not having had more than 5 cigarettes between two weeks after enrolment and follow-up, in line with Russell standards [77]. Unsuccessful quit attempts in the past six months will also be recorded. In line with the feasibility trial, smoking reduction in cigarette consumption by 50% or in CO reading by 30% will be assessed at both 1- and 6-month follow-up.
- 4.5.2.2 Clinical (mental health-related) outcomes: At 6-month follow-up only, general and mental health functioning will be assessed using measures detailed in 3.8.1.3.
- 4.5.2.3 Practical (design-related) outcomes: As in Phase I, attrition and, in the intervention group, adherence rate will be assessed at 1-month follow-up. Attrition will also be assessed at 6-months follow-up, in addition to continued use of e-cigarettes in the intervention group and de novo e-cigarettes use in the control group.
- 4.5.2.4 Psychosocial outcomes: Health-related quality of life will be assessed using EQ-5D-5L [82] and the mental health specific ReQoL [83] at final follow-up. Health and social care service use will be measured using the Client Service Receipt Inventory (CSRI), which has been validated against objective primary care records [84] and is also recommended for usage of hospital and other community health services [85]. Changes from baseline in other health behaviours (see 3.8.1.4) will be determined at 6-month follow-up.
- 4.5.2.5 Cost effectiveness: To determine short-term cost-effectiveness of the intervention, we will undertake a within-trial incremental cost-effectiveness analysis to assess the value

for money afforded by the intervention over and above the usual care using data collected during the trial. A service use questionnaire piloted in the feasibility workstream will be used to collect resource use at baseline, one and six months and will include both the cost of providing the interventions and the costs of patients' health care utilisation from an NHS perspective as recommended by NICE technology appraisal guide [86]. To assess long-term cost, effectiveness, we will undertake economic modelling (see 4.7).

4.5.2.6 Serious adverse events: Serious adverse events will be monitored, recorded and assessed as per the procedure outlined in Phase I throughout the study.

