3.8 Measures

3.8.1 Baseline measures

Baseline measures will be collected via a brief questionnaire and health records.

- *3.8.1.1 Socio-demographic characteristics:* These include age, sex, employment status, ethnicity, education, employment, accommodation type and marital status.
- 3.8.1.2 Smoking-related characteristics: These include general smoking characteristics, quit attempts and methods (including e-cigarettes), nicotine dependence [53], strength of urges to smoke (SUTS) [54], motivation to quit [55] and adexhaled breath carbon-monoxide (CO) reading.
- 3.8.1.3 General and mental health-related characteristics: These include most recent diagnosis (if available), antipsychotic medication use, and acute events (e.g. hospitalisation) in the last year. Mental health symptoms will be assessed with the PHQ-9 [56], GAD-7 [57] and SF-12 questionnaires [58].
- 3.8.1.4 Health behaviour characteristics: Alcohol use [59], exercise [60] and diet [61] will be assessed.

3.8.2 Primary outcome measures:

3.8.2.1 Feasibility and acceptability outcomes: The primary feasibility outcome measures in the feasibility trial will be consenting rate and recruitment frequency. Consenting rate will be calculated from the number of eligible participants approached who consent to take part in the study. The criterion to judge whether a large-scale RCT is feasible using the proposed recruitment approach is consenting a minimum of ~15% of eligible participants (see 3.14) which is slightly lower than the consenting rate typical in clinical trials in general patient populations in the UK [62]. Recruitment frequency will be calculated as the number of eligible patients at each site who agree to participate in the trial per month. Based on our projection of the number of participating trusts and sites in the full RCT, we would require around six participants per month from each Trust to deliver the full RCT successfully (see 3.9/4.4). MHR (or CPN) will be asked to record the number of non-eligible patients using a check list of common reasons for exclusions.

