4.7.2 Cost-effectiveness

To determine short-term cost-effectiveness, we will combine the cost data with health outcomes expressed in quality-adjusted life years (QALYs) measured using EQ-5D-5L to calculate the incremental cost effectiveness ratio (ICER) [90]. We will assess the cost-effectiveness of the intervention by comparing the ICER with the NICE willingness-to-pay (WTP) thresholds range of £20,000-£30,000 per QALY gained [86]. Missing data will be handled by multiple imputation method following Rubin's rules [91]. The imputation will be performed using chained equations by trial arms, assuming any missing data is missing at random. A non-parametric bootstrap re-sampling technique will be used to test the uncertainty of the calculated ICERs (117-120). Based on the results of 5,000 bootstrap replicates, we will plot the probabilities of the intervention being cost-effective over various WTP thresholds on cost-effectiveness acceptability curves [92].

Health economic modelling will be applied to establish long-term cost-effectiveness, beyond the time horizon of the project. The health economists involved in this application have pioneered the use of decision models to judge longer term health impact and cost effectiveness in this area [93, 94]. Based on a decision analytical model developed at the University of York, we will construct a Markov model to make long-term projections of both health gain and health care costs associated with the two trial interventions [93, 94]. The long-term costs are calculated based on the healthcare resources used for treating smoking-related diseases for smokers and quitters, by age and gender [95, 96]. We will employ the cost-of-illness methods introduced by the WHO Economics of Tobacco Toolkit [97] using appropriate reference data [98] and incorporating relapse for quitters [99-101]. The results of the model will provide information with regard to long-term value for money and can be compared to the NICE decision-making threshold. The model will incorporate uncertainty using probabilistic sensitivity analysis and we will demonstrate the probability that ESCAPE would be a cost-effective use of health care resources.

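### No baseline EQ-5D-5L is scheduled for Phase II, so the QALYs behind the within-trial ICER have no measured starting utility

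*Protocol*

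**What the plan says.** Protocol 4.5.2.4 (psychosocial outcomes, Phase II): "Health-related quality of life will be assessed using EQ-5D-5L [82] and the mental health specific ReQoL [83] at final follow-up". No other section gives EQ-5D-5L a time point.

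The heading of 4.5 sends the reader back to the Phase I list for baseline: "4.5 Measures (see 3.8.1 for baseline measures". In that list, 3.8.1.3 covers health status: "Mental health symptoms will be assessed with the PHQ-9 [56], GAD-7 [57] and SF-12 questionnaires [58". Neither EQ-5D-5L nor ReQoL appears anywhere in 3.8.1.

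Protocol 4.7.2 takes the effect side of the within-trial analysis from this instrument: "combine the cost data with health outcomes expressed in quality-adjusted life years (QALYs) measured using EQ-5D-5L to calculate the incremental cost effectiveness ratio (ICER". On the cost side, 4.5.2.5 says that the service-use questionnaire "will be used to collect resource use at baseline, one and six months".

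Missing data in the economic analysis are to be handled by chained-equation multiple imputation within arms under a missing-at-random assumption, and the ICER is judged against £20,000 to £30,000 per QALY (4.7.2).

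**The concern.** A QALY is utility accumulated over time. To compute it over six months one needs a value at the start as well as at the end. The protocol schedules three cost measurements but only one utility measurement, so the two halves of the ICER do not rest on the same observation period.

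The gap lies in data collection, not in analysis detail. A later analysis plan can choose a formula, but it cannot supply a baseline utility that nobody was asked for, and imputation cannot fill in a variable that is unobserved for every participant. Phase I would not reveal the gap either, because 3.8.3.4 pilots the service-use questionnaires and not EQ-5D-5L.

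Cost-effectiveness is part of the main aim in section 2. At stake are the size of the incremental QALY, which comes to depend on an untestable assumption, and the precision of the estimate.

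**Working it through.** No figure in the protocol depends on this point, so there is nothing to reproduce. The check has a textual part and an illustrative calculation.

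**Text, side by side**

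| Item | Baseline | 1 month | 6 months | Source |
|---|---|---|---|---|
| EQ-5D-5L | not stated | not stated | yes | 4.5.2.4; absent from 3.8.1 |
| Service use (costs) | yes | yes | yes | 4.5.2.5 |
| SF-12, PHQ-9, GAD-7 | yes | no | yes | 3.8.1.3; 4.5.2.2 |
| Other health behaviours | yes | no | yes | 3.8.1.4; 4.5.2.4 |

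Where a baseline comparison is meant, 4.5.2.4 says so in the same paragraph: "Changes from baseline in other health behaviours (see 3.8.1.4) will be determined at 6-month follow-up". It says nothing similar for EQ-5D-5L.

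**Inputs**
- From the protocol: 370 per arm (4.6), follow-up T = 0.5 years, threshold £20,000 per QALY (lower end, 4.7.2).
- Assumed, not in the protocol: utility SD 0.20 to 0.30, equal at both times; baseline to 6-month correlation r of 0.5 to 0.7; an illustrative 6-month utility gain of 0.02.

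**Step 1: the two ways to make a QALY from one value.** Let Δ be the between-arm difference in 6-month utility.
- Common assumed baseline, linear path: QALY = 0.5 × (u0 + u6)/2, so the incremental QALY is 0.25 × Δ = 0.25 × 0.02 = 0.005.
- 6-month value applied throughout: QALY = 0.5 × u6, so the incremental QALY is 0.5 × Δ = 0.5 × 0.02 = 0.010.

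The ratio is 0.5/0.25 = 2 for any Δ. At the same incremental cost, the first ICER is twice the second. The protocol's threshold range spans a factor of only 30,000/20,000 = 1.5.

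**Step 2: chance baseline imbalance.** SE(d) = SD × √(2/370) = SD × 0.0735, which is 0.0147 at SD 0.20 and 0.0221 at SD 0.30.

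**Step 3: how imbalance reaches the incremental QALY.** With baseline unmeasured, an imbalance d enters only through 6-month utility, as about r × d. For one SE:
- Common baseline: 0.25 × r × SE(d). Low end 0.25 × 0.5 × 0.0147 = 0.0018; high end 0.25 × 0.7 × 0.0221 = 0.0039 QALY. At £20,000 per QALY this is about £37 to £77 per participant.
- 6-month value throughout: 0.5 × r × SE(d), twice as large: 0.0037 to 0.0077 QALY, about £74 to £154.

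**Step 4: precision.** Adjusting for baseline utility leaves a fraction 1 − r² of the variance of 6-month utility: 0.75 at r = 0.5 and 0.51 at r = 0.7. The reduction is therefore 25 to 49%.

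**The case against.** **Baseline may be implied.** The sentence in 4.5.2.4 does not say that final follow-up is the sole time point. In 4.5.2.2 the wording restricts the mental health measures to the 6-month follow-up, although 3.8.1.3 also takes them at baseline, so naming a follow-up time in 4.5.2 does not exclude baseline. The 3.8.1 list is also incomplete for Phase II, since it omits service use, and 4.2 promises "expanded questionnaires to assess all secondary outcomes relevant for a full RCT (see 2.5"). This stands to the extent that a reader who infers a settled decision to leave baseline out goes beyond the text. It does not close the gap. Service use is expressly given a baseline in 4.5.2.5 while EQ-5D-5L is not. The promise in 4.2 names no instrument or time point, and its cross-reference leads to no existing section.

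**Randomisation and other measures help.** Randomisation keeps the 6-month utility comparison unbiased on average, and chance imbalance is already part of its standard error. SF-12, PHQ-9 and GAD-7 at baseline can serve as covariates and imputation predictors. Both statements are right. A reader might infer that nothing can be adjusted afterwards, but partial adjustment is possible. Those measures do not give a QALY starting value, however, and the protocol plans no utility derived from SF-12.

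**Size.** A reader might infer that imbalance could reverse the sign of the ICER. The protocol gives no expected cost or QALY difference, so this cannot be shown. Nor should the full imbalance be weighted by 0.25 years: that describes a baseline that was measured and left unadjusted.

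**Burden.** 3.8.3.1 treats questionnaire burden as a possible barrier and foresees prioritising measures. That is a reason to keep the remedy small.

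**Conclusion.** The point holds as a gap in the schedule: no baseline EQ-5D-5L is stated, while 4.7.2 needs one. The analyst is left with two assumptions whose incremental QALYs differ two-fold whatever the true 6-month difference (0.005 against 0.010 for an assumed gain of 0.02).

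The loss is the QALY starting point, direct adjustment for chance imbalance, and precision; bias in the 6-month comparison is not the problem. The monetary ranges and the 25 to 49% variance reduction rest on the assumed SD and correlation and are illustrations. SF-12, PHQ-9 and GAD-7 could recover only part of that precision.

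This should be fixed, but it does not threaten the trial's main result. Cost-effectiveness is in the main aim, yet 4.1.2 lists it among the secondary objectives, and the primary outcome, its power and the clinical analyses are untouched. The change has to come before Phase II baseline data are collected, because the missing values cannot be recovered later.

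**What to change.** 1. Add EQ-5D-5L to the Phase II baseline questionnaire, and say so in 3.8.1 (or in a Phase II baseline list under 4.5) and in 4.5.2.4. If baseline administration was always intended, one added line settles it.
2. State in 4.7.2 that QALYs are computed as the area under the utility curve, that incremental QALYs are estimated with adjustment for baseline utility, and that baseline utility enters the imputation model.
3. Optional: add EQ-5D-5L to the 1-month survey so that utilities follow the same schedule as resource use. The QALY can be repaired without it.

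Extra ReQoL administrations are not needed for the ICER. The cost is five short items at a contact that already takes place (3.6.3).
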